7.6.1. Analysis of Categorical Endpoints

Analyses of other categorical efficacy endpoints will be conducted using the stratified CMH approach described for the efficacy endpoints of primary interest. Response will be summarized for each treatment group by visit as the proportion of subjects in the category of interest at the specified visit, and across the 24-week treatment period as the proportion of subjects in the

category of interest at any time during treatment. The difference in proportions between the ALPN-101 treatment group and the placebo group and the associated 95% CI for this difference will be reported.

7.6.2. Analysis of Continuous Endpoints

MMRM will be used for the analysis of continuous longitudinal data. Terms in the model will include treatment group, baseline value of the analysis variable, stratification factors (concomitant oral immunosuppressive therapy use at enrollment and geographic region), analysis visit, and the interactions of treatment-by-visit and baseline value-by-visit as fixed effects. An unstructured covariance matrix will be used to model within-subject error. If the model fails to converge with an unstructured covariance matrix, a heterogeneous compound symmetric structure will be used. Kenward-Roger degrees of freedom, Type III sums of squares, and least squares (LS) mean values will be reported for each treatment group and for the difference between treatments. Standard errors and 95% CI for the estimated mean difference at each visit will be presented. Plots of LS mean values and 95% CIs by visit with separate lines for each treatment group will be provided for continuous secondary efficacy endpoints.

Annualized flare rates and cumulative prednisone-equivalent dose use will be analyzed using an analysis of variance model. Terms in the model include treatment group and stratification factors (concomitant oral immunosuppressive therapy use at enrollment and geographic region). Type III sums of squares, and least squares (LS) mean values will be reported for each treatment group and for the difference between treatments. Standard errors and 95% CI for the estimated mean difference will be presented.

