5. ANALYSIS POPULATIONS AND SUBGROUPS

5.1. Analysis Populations

The following analysis populations will be used for the analysis of study data.

- All Randomized Population: The randomized population will include all subjects who are assigned to study treatment, regardless of whether study treatment is received. The randomized population will be analyzed according to the treatment group into which they were randomized, regardless of the actual treatment received.
- Modified Intent-to-Treat Population: The modified intent-to-treat (mITT) population includes all randomized subjects who received any amount of study drug and completed at least one post-baseline disease assessment. mITT subjects will be analyzed according to the treatment group into which they were randomized, regardless of the actual treatment received. Unless otherwise specified, this population will be used for the analysis of efficacy endpoints.
- **Safety Population:** The safety population includes all subjects who received any amount of study drug. The safety population will be analyzed by treatment actually received. Unless otherwise is specified, this population will be used for the analysis of safety endpoints.
- **Pharmacokinetics Population:** The PK population includes all subjects who received at least one dose of ALPN-101 and have at least one post-dose PK concentration reported. Unless otherwise is specified, this population will be used for the analysis of PK endpoints.
- Anti-Drug Antibodies Population: The ADA population includes all subjects who received at least one dose of study drug and have at least one post-baseline ADA value.

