6.10. Annualized Flare Rate

The annualized flare rate for each subject is defined as the number of flares observed during the treatment period divided by the flare exposure time in days multiplied by 365.25. Flare exposure time of a subject is defined as the difference in days between the last BILAG-2004 assessment date and the date of first dose + 1. For subjects who do not experience any flares for each of the SLE flare definitions, then the number of flares for that subject will be set to zero for each definition.

[figure not shown]
Annualized flare rate will be calculated for each definition of SLE flare.

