7.4.2. Handling of Missing Data and Intercurrent Events (IE)

Intercurrent events in this study include the following:

- IE1: Premature discontinuation of study treatment
- IE2: Restricted/rescue medication use (criteria for restricted/rescue medication use is provided in Section 6.21)

The strategies to be used in the handling of intercurrent events and missing data for efficacy endpoints, when applicable, are provided below:

- Binary endpoints (primary and secondary efficacy endpoints):
 - IE1 and IE2: subject is considered a non-responder (composite strategy)
 - Missing data for Day 169: subject is considered a non-responder
- Continuous endpoints measured through time (SLEDAI-2K total score):
 - IE1 and IE2: data after IE1 and IE2 occurs will not be included in the analysis (hypothetical strategy)
 - Missing data caused by applying the intercurrent event handling described above and other missing data will be handled by the mixed effects models for repeated measures (MMRM) analysis
- Other efficacy endpoints:
 - Treatment policy strategy will be applied and all observed data during the treatment period will be used regardless of IE1 or IE2
 - Missing data for Day 169 for binary endpoints: subject is considered a non-responder for applicable endpoints

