7.7. Estimands for the Primary and Secondary Endpoints

Estimand definitions for the primary and secondary efficacy endpoints are provided below:

Table 2: Estimand Attributes Corresponding to the Primary and Secondary Efficacy Endpoints

	Attributes of the Estimand						
Estimand	Treatment	Endpoint	Population	Handling of Intercurrent Events	Statistical Summary		
Primary	ALPN-101 vs. Placebo	Achievement of SRI-4 response at Day 169	Subjects with moderate to severe SLE	IE1 and IE2: subject is considered a non-responder (composite strategy) Missing data: subject is considered a non-responder	Difference in the proportion of subjects achieving SRI- 4 response		
Primary	ALPN-101 vs. Placebo	Achievement of BICLA response at Day 169	Subjects with moderate to severe SLE	IE1 and IE2: subject is considered a non-responder (composite strategy) Missing data: subject is considered a non-responder	Difference in the proportion of subjects achieving BICLA response		
Secondary	ALPN-101 vs. Placebo	Annualized flare rate by BILAG- 2004 flare index through Day 169 for all flares	Subjects with moderate to severe SLE	All observed data used (treatment policy strategy)	Difference in the LS means for annualized flare rate by BILAG-2004 flare index for all flares		
Secondary	ALPN-101 vs. Placebo	Time-to-first flare by BILAG- 2004 flare index	Subjects with moderate to severe SLE	All observed data used (treatment policy strategy)	Hazard ratio for time-to- first flare by BILAG-2004 flare index		
Secondary	ALPN-101 vs. Placebo	Achievement of LLDAS response at Day 169	Subjects with moderate to severe SLE	IE1 and IE2: subject is considered a non-responder (composite strategy) Missing data: subject is considered a non-responder	Difference in the proportion of subjects achieving LLDAS response		

	Attributes of the Estimand						
Estimand	Treatment	Endpoint	Population	Handling of Intercurrent Events	Statistical Summary		
Secondary	ALPN-101 vs. Placebo	Change from baseline in SLEDAI-2K total score at Day 169	Subjects with moderate to severe SLE	All observed data used (hypothetical strategy)	Difference in the LS means for change from baseline in SLEDAI- 2K total score		
Secondary	ALPN-101 vs. Placebo	Cumulative prednisone- equivalent dose use through Day 169	Subjects with moderate to severe SLE	All observed data used (treatment policy strategy)	Difference in the LS means for cumulative prednisone- equivalent dose use		

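### ANOVA on per-subject annualized flare rates lets short follow-up dominate the estimate, and can produce a false difference if flare-related stopping differs between arms

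*SAP*

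**What the plan says.** SAP 6.10 defines the subject-level rate as the "number of flares observed during the treatment period divided by the flare exposure time in days multiplied by 365.25". Exposure is the "difference in days between the last BILAG-2004 assessment date and the date of first dose + 1". Subjects without a flare are given a count of zero.

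SAP 7.6.2 then states: "Annualized flare rates and cumulative prednisone-equivalent dose use will be analyzed using an analysis of variance model". The only terms are treatment and the two stratification factors. Table 2 in SAP 7.7 gives the summary measure as "Difference in the LS means for annualized flare rate by BILAG-2004 flare index for all flares".

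Three other provisions bear on how long exposure lasts:

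- SAP 7.4.2, for endpoints in this group: "Treatment policy strategy will be applied and all observed data during the treatment period will be used regardless of IE1 or IE2". Table 2 agrees.
- SAP 7.6 instead limits the secondary analyses, for subjects who stop treatment early, to assessments within 28 days of stopping.
- SAP 5.1 admits to mITT any treated subject who "completed at least one post-baseline disease assessment". It does not require that assessment to be a BILAG.

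**The concern.** A ratio computed for each subject and averaged with equal weight treats a rate measured over one month as being as informative as a rate measured over six. Because exposure is the denominator, a flare shortly before a subject leaves produces a very large value.

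The documents give a route from flare to short follow-up. Protocol 8.2.2.3 discontinues study drug when background therapy plus permitted steroid bursts is inadequate, and SAP 7.6 then cuts the data 28 days later. If that happens more often in one arm, the ANOVA can report a difference in flare rate where the true rates are equal.

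At stake is the interpretation of a secondary efficacy endpoint in a study whose enrollment stopped at 76 subjects, about 38 per arm. At that size, a few short-exposure subjects can carry much of the variance.

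**Working it through.** **Inputs from the documents.** BILAG is done at Baseline and on Days 29, 57, 85, 113, 141, 169 and 197, but not on Day 15 (Protocol Table 1, footnotes 10 and 12). Enrollment stopped at 76 (SAP 4.1). The documents give no flare rate, dispersion, dropout or power for this endpoint, so there is no plan figure to reproduce. SAP Table 1 covers only SRI-4 and BICLA.

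**Step 1: value of a single flare.** Rate = 1 / exposure days × 365.25.

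| Last BILAG | Rate per year |
|---|---|
| Day 29 | 365.25/29 = 12.59 |
| Day 57 | 365.25/57 = 6.41 |
| Day 85 | 365.25/85 = 4.30 |
| Day 169 | 365.25/169 = 2.16 |

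The same event counts 169/29 = 5.8 times as much at Day 29 as at Day 169.

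**Step 2: the subject never assessed for flare.** Suppose the only post-baseline visit is Day 15 (SLEDAI-2K and PhGA). The subject is in mITT. If the Day 1 BILAG is taken as the last one, exposure is 1 day, the count is zero, and the subject enters as 0/yr with full weight.

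**Step 3: mismatched periods.** Flares are counted in the treatment period, but the last BILAG can be on Day 197. One flare would then give 365.25/197 = 1.85/yr instead of 2.16/yr, which is 14% lower.

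**Step 4: the 28-day cut.** SAP 7.6 does not say whether discontinuation is dated from the last dose. If it is, a flare found before dosing on Day 57 has last dose Day 43 and cutoff Day 43 + 28 = Day 71. The Day 85 BILAG is excluded, and scheduled follow-up for this endpoint ends at the flare visit.

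**Step 5: simulation under no treatment effect.** Assumed, not in the documents: the flare rate, gamma frailty variance 0.5, 2% random loss per visit, and the chance of leaving after a flare. The ANOVA is represented by a two-sample t-test without strata terms. The comparator is negative binomial regression with log exposure as offset. The table shows rejection rates at 0.05 for 2 flares/yr and 38 per arm. With 1,500 runs per row, the Monte Carlo standard error at 5% is √(0.05×0.95/1500) = 0.6 points.

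| Leave after a flare, ALPN-101 / placebo | Follow-up ends | ANOVA | Negative binomial |
|---|---|---|---|
| 30% / 30% | at the flare visit | 4.8% | 4.3% |
| 10% / 30% | at the flare visit | 7.6% | 5.2% |
| 10% / 50% | at the flare visit | 12.6% | 4.6% |
| 0% / 50% | at the flare visit | 19.9% | 4.9% |
| 10% / 50% | one visit later | 6.5% | 4.9% |

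At 1.5 flares/yr with the same frailty, ANOVA error is 9.3% for 10% versus 40% and 11.5% for 10% versus 50%. With no frailty these become 11.8% and 16.1%. With one more BILAG after the flare, 10% versus 40-50% gives about 6.5 to 7%.

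**Step 6: bias and power at a true 2/yr.** Leaving at 10% versus 50% gives mean rates of 2.18 and 2.87, a false difference of 2.18 − 2.87 = −0.69/yr. With 30% leaving in both arms the means are 2.54 and 2.55: both inflated, with no false difference. For true rates of 1 versus 2/yr and 30% leaving in both arms, power is 43% for the ANOVA and 52% for a ratio of total flares to total person-time with a robust standard error.

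**Step 7: influence of subjects with 57 days or less, over 1 to 3 flares/yr.** With 30% leaving at the flare visit in both arms, 8-17% of subjects supply 35-39% of the mean and 51-61% of the sum of squares. With one more visit the shares are 16-20% and 26-28%. With random loss only, 4% of subjects supply 4% of the mean and 10-13% of the sum of squares.

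**The case against.** The strongest reply is that the documents work against follow-up ending at the flare. Permitted steroid bursts do not require stopping study drug (Protocol 8.2.2.3). Subjects who stop drug are asked to complete the End of Treatment assessments and stay on the visit schedule (Protocol 4.3.2 and 6.6.1), and Table 2 uses all observed data. The flare count includes mild flares, and no figure in the documents supports 40-50% of flares ending follow-up at once. This stands, and it limits the size of the problem: one further BILAG removes most of the excess error. It does not settle the matter, because the SAP 7.6 cut contradicts the treatment policy strategy and withdrawal of consent still shortens exposure.

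It is also fair that the Day-15-only subject is an edge case. End of Treatment or End of Study procedures would usually supply a BILAG, and the 1-day exposure is an inference from the wording of SAP 6.10.

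On importance, the sample size was not derived for formal efficacy testing, there is no multiplicity control, and the Cox model for time to first flare already handles variable follow-up for first flares. These points lower the grade. They do not make equal weighting of unequal exposures a good choice.

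A reader might infer that events over person-time are unbiased. They are not, if subjects differ in flare propensity, because flare-driven stopping then removes high-rate person-time. The median negative binomial rate ratio was 1.04 under the null at 10% versus 50% stopping. With frailty variance 1, person-time rates of 1.32 and 1.22 were seen under equal true rates, a ratio of 1.32/1.22 = 1.08.

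**Conclusion.** The weakness is real but conditional. The specified ANOVA makes each subject's influence depend on when follow-up ended, so short follow-up can dominate the estimate. Stopping at or near a flare inflates mean rates in both arms and costs power.

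Two stronger readings are tempting, and the documents do not support them. One is that short follow-up always dominates: under random loss, or where visits continue after a flare, it does not. The other is that flare-related withdrawal in itself creates a false treatment difference: if it is equal between arms, type I error stays at about 5%.

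With unequal stopping at the flare visit (10% versus 40-50%), error at 38 per arm and 1.5 to 2 flares/yr is about 8 to 14%, reaching about 16% in a run with no between-subject variation. It is about 5 to 8% if one more BILAG follows. These figures rest on assumed stopping fractions, flare rates and frailty. The direction of any bias depends on which arm leaves more after flares; it favors ALPN-101 if that is placebo. That the ANOVA is unweighted is inferred from the absence of any stated weight.

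This should be fixed, but because it affects a secondary endpoint with no confirmatory claim it does not threaten the study.

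**What to change.** - **Model (SAP 7.6.2 and Table 2).** Analyse the flare count by negative binomial regression with log(flare exposure time) as offset, and treatment, background therapy and pooled region as terms. Report the rate ratio and model-based annualized rates with 95% CIs. Keep the ANOVA as supportive.
- **Subjects.** Exclude from this endpoint those with no post-baseline BILAG, and report their number by arm.
- **Data cut.** Reconcile the 28-day limit in SAP 7.6 with the treatment policy strategy in SAP 7.4.2 and Table 2, since this decides how often short denominators occur.
- **Exposure period (SAP 6.10).** End exposure where flare counting ends, through Day 169, so that the Day 197 BILAG does not lengthen the denominator.

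The cost is SAP wording and one standard procedure call. The effect measure becomes a rate ratio, and the new model greatly reduces, but does not fully remove, bias from flare-driven stopping when subjects differ in flare propensity.

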- 6. The Investigator's preliminary determination of organ system activity at Screening must be verified by the Sponsor or their designee to confirm eligibility. The Investigator will determine and confirm eligibility at Baseline (i.e., Day 1 prior to randomization).
- 7. Subjects must be on appropriate SOC (i.e., at least one anti-malarial or an immunosuppressant) for SLE, based on the Investigator's judgement. If taking the following medications, the subject must be on a stable dose prior to Baseline (i.e., Day 1 prior to randomization) for the period of

time specified below, and must intend to continue at stable doses throughout the 24-week Treatment Period, unless otherwise specified by this protocol:

- Corticosteroids: stable between Screening and Baseline (NOTE: dose must not be greater than 20 mg/day prednisone or equivalent).
- Hydroxychloroquine/hydroxychloroquine-like drugs: stable between Screening and Baseline (NOTE: dose must not be greater than 400 mg daily hydroxychloroquine or equivalent).
- NSAIDs or cyclooxygenase-2 (COX-2) inhibitors that are used continuously (at or below the maximum approved dose, and with approval by the Sponsor or designee): stable for 14 days prior to Baseline; the requirement for stable and continuous use does not apply to NSAIDS that are used intermittently for management of pain.

Subjects who are using NSAIDs infrequently or "as needed" should make every attempt to withhold dosing on study visit days until SLE assessments have been completed.

For the following drugs, subjects must be on stable doses for 4 weeks prior to Screening until Baseline and for the remainder of the study:

- Methotrexate (7.5–25 mg weekly)
- Azathioprine (50–150 mg daily)
- Leflunomide (10–20 mg daily)
- 6-Mercaptopurine (50–200 mg daily)
- Mycophenolate mofetil (500–2000 mg daily)
- Mycophenolic acid (360–1440 mg daily)
- Permitted dose and stability period for agents not listed here, but not specifically
 excluded by this protocol, require discussion with, and agreement by, the Medical
 Monitor
- 8. Willing to provide consent for serial photographic documentation of any cutaneous manifestations of SLE, and/or oral mucocutaneous lesions (including aphthous ulcers) not attributed to SLE, from Screening through the EoS.

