6.6. Unscheduled Visits

6.6.1. Early Termination

If a subject withdraws consent for study participation prior to Day 197, the EoS evaluations should be completed if possible, preferably within 2 weeks of study drug discontinuation. In addition, a follow-up phone call should occur 8 weeks after the last dose of study drug to determine the status of any ongoing AEs/SAEs or the occurrence of any new AEs/SAEs.

As noted in §4.3, subjects who prematurely discontinue treatment with study drug (i.e., due to subject choice, Investigator decision, an AE or other contraindication for ongoing receipt of study drug, etc.), and who do not withdraw consent, should have all procedures outlined in the EoT visit as well as an unscheduled ECG, as soon as possible, preferably within 2 weeks. Afterwards, subjects should resume following the regular visit schedule as outlined in Table 1, and adhere to all study procedures except for study drug dosing. As the subject has discontinued study drug, all concomitant medication restrictions as outlined in §8.2.2 no longer apply. If at any point subsequently a subject no longer wants to provide assessments (withdrawal of consent) following discontinuation of study drug and completion of the EoT assessments, an EoS visit is not required.

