3.1.2. Secondary Efficacy Endpoints

Secondary efficacy endpoints are provided below:

- Annualized flare rate by British Isles Lupus Assessment Group (BILAG)-2004 flare index through Day 169 all flares
- Time-to-first flare by BILAG-2004 flare index
- Achievement of Lupus Low Disease Activity State (LLDAS) at Day 169
- Change from baseline in Systemic Lupus Erythematosus Disease Activity Index 2000 (SLEDAI-2K) total score at Day 169
- Cumulative prednisone-equivalent dose use (total area under the curve of daily prednisone-equivalent dose) through Day 169
- Achievement of ≥50% reduction in Cutaneous Lupus Erythematosus Disease Area and Severity Index (CLASI) activity score at Day 169 in the subgroup of subjects with baseline CLASI activity score ≥8

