4.3. Methods of Assigning Subjects to Treatment

A centralized interactive web-based response system will be used to randomly assign subjects to receive either ALPN-101 or placebo in a 1:1 ratio. Randomization will be stratified by geographic region and by use of concomitant oral immunosuppressive therapy at enrollment. Levels of each stratification factor, which result in 6 unique strata, are defined as follows:

- 1. Background immunosuppressive therapy use:
 - Present: Concomitant use of at least one of the permitted immunosuppressants (e.g., methotrexate, leflunomide, azathioprine, 6-mercaptopurine, mycophenolate mofetil, mycophenolic acid) and/or corticosteroids at doses >5 mg prednisone or equivalent daily with or without hydroxychloroquine/hydroxychloroquine-like drugs;

^{*}Assuming a 2-sided significance level of 0.05 using SAS version 9.4

• Absent: No use of permitted immunosuppressants and/or corticosteroids at doses >5 mg prednisone or equivalent daily, with or without use of lower doses of corticosteroids and/or hydroxychloroquine/hydroxychloroquine-like drugs.

2. Geographic region:

- Region 1: North America or Western Europe
- Region 2: Eastern Europe
- Region 3: Asia

Subjects, investigators, site staff, and individuals with direct contact with site staff (e.g., clinical research associates, project management, medical monitors, and data management) will remain blinded to treatment assignment until after final database lock. Select study team members may be unblinded to treatment assignment. A list of all individuals unblinded to treatment assignment prior to final database lock will be maintained.

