7.6. Analysis of Secondary Efficacy Endpoints

Unless otherwise stated, the mITT population will be the basis for analyses of all efficacy endpoints. These data will be analyzed through Week 24 (Day 169) for subjects who complete treatment and through the last assessment recorded \leq 28 days after treatment discontinuation for subjects who discontinue treatment early.

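### The analysis of cumulative prednisone-equivalent dose leaves out baseline daily dose and gives up precision at 76 subjects

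*SAP*

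**What the plan says.** SAP 3.1.2 lists the endpoint as "Cumulative prednisone-equivalent dose use (total area under the curve of daily prednisone-equivalent dose) through Day 169". It is a total, not a change from baseline. SAP 7.6.2 assigns it, with annualized flare rate, to an analysis of variance: "Terms in the model include treatment group and stratification factors (concomitant oral immunosuppressive therapy use at enrollment and geographic region". The repeated-measures model in the same section does adjust for the baseline value.

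On entry dose, Protocol 5.1 (criterion 7) has "Corticosteroids: stable between Screening and Baseline (NOTE: dose must not be greater than 20 mg/day prednisone or equivalent". Steroids are not required, so the range is 0 to 20 mg/day. Protocol 4.1 and 8.2.2 keep the dose stable through Day 169 except for toxicity, short bursts that return to the Day 1 dose, and a discretionary taper after Day 85.

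On the stratum, SAP 4.3 counts as present any permitted immunosuppressant "and/or corticosteroids at doses >5 mg prednisone or equivalent daily with or without hydroxychloroquine/hydroxychloroquine-like drugs".

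On data after stopping study drug, three places matter:
- SAP 7.4.2: "Treatment policy strategy will be applied and all observed data during the treatment period will be used regardless of IE1 or IE2"; Table 2 in SAP 7.7 repeats "All observed data used (treatment policy strategy" for this endpoint.
- SAP 7.6 instead ends the data at the last assessment no more than "28 days after treatment discontinuation for subjects who discontinue treatment early".
- Protocol 6.6.1: "As the subject has discontinued study drug, all concomitant medication restrictions as outlined in §8.2.2 no longer apply".

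**The concern.** A subject who enters on 15 mg/day and follows the protocol accumulates far more steroid than one who enters on none, whichever arm each is in. That difference is known before randomization and has nothing to do with treatment, yet the model leaves most of it in the error term. The stratum does not replace it: a subject on methotrexate without steroids sits in the same level as one on 20 mg/day.

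Randomization protects the comparison from bias due to the omission, and type I error is not inflated. What is lost is precision, and SAP 4.1 records that enrollment stopped at 76 of a planned 130. The estimate also becomes hard to read if the arms differ by chance in entry dose. Each 1 mg/day of imbalance left after stratum adjustment moves it by up to 169 days × 1 mg/day = 169 mg.

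**Working it through.** **The plan's own figure.** There is none for this endpoint: no SD, effect size or power. The stated 82% and 87% power concern SRI-4 and BILAG response at 65 per arm and do not bear on this point.

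**Formula.** With N = 76 and region pooled to two levels (SAP 7.4.1), residual degrees of freedom are 76 − 4 = 72 without the covariate and 71 with it. If ρ is the correlation of baseline dose with cumulative dose within strata, then

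SE(with) / SE(without) = √(1 − ρ²) × √(72/71).

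The number of subjects the unadjusted model would need to match is 76 / ratio².

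| ρ | SE ratio | Interval narrower by | Unadjusted N to match |
|---|---|---|---|
| 0.3 | 0.96 | 4% | about 82 |
| 0.5 | 0.87 | 13% | about 100 |
| 0.7 | 0.72 | 28% | about 147 |
| 0.8 | 0.60 | 40% | about 208 |
| 0.9 | 0.44 | 56% | about 394 |

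If ρ = 0 the cost is √(72/71) = 1.007, under 1% of the standard error.

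**Which ρ is plausible.** The documents do not say, so dose histories were simulated under the protocol's steroid rules at N = 76. All of the following are assumptions:
- baseline SD 3.2, 5.1 or 6.4 mg/day, 22% on no steroid; immunosuppressant use 15% or 50%
- mean 0.2, 0.5 or 1.0 bursts per subject; 25% of users tapering after Day 85
- 10, 20 or 30% stopping study drug, uniformly over Days 14 to 155; 0, 25 or 50% of them then taking 20 to 40 mg/day
- parenteral courses of 600 to 3,750 mg prednisone-equivalent in none or 5% of subjects

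Ratio of SE **without** to SE **with** baseline dose:

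| Data used | No parenteral courses | With parenteral courses |
|---|---|---|
| Cut 28 days after stopping | 1.4 to 3.4 (median 2.2) | 1.15 to 1.9 |
| All observed, 25 to 50% of discontinuers escalate | 1.07 to 2.6 (median 1.4) | 1.05 to 1.7 |
| All observed, no escalation | 2.0 to 5.0 | 1.2 to 2.0 |

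In a heavy case (all observed data, 30% stop and all escalate, mean one burst) the ratio was 1.03 to 1.2.

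**One case in milligrams.** SD 5.1, 50% on an immunosuppressant, 20% stopping, 25% of those escalating, no parenteral courses:
- 28-day cut: SE 162 without and 67 with; 162/67 = 2.4.
- All observed data: SE 201 and 119; 201/119 = 1.7. The 95% half-widths are about 400 and 238 mg.

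A repeat gave 170 and 70 mg with the cut, and 197 and 123 mg with all observed data. Coverage of the unadjusted interval was about 0.95.

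**Check under different assumptions.** A second simulation used 20 to 40% on no steroid, 30 to 60% on an immunosuppressant, 30 to 50% tapering and 0 to 30% stopping. The strata explained only 14 to 35% of the variance in baseline dose. Values of ρ were:
- bursts and tapers only: 0.94 to 0.98
- 28-day cut: 0.89 to 0.94
- 15% stopping with a mean extra 10 mg/day afterwards: 0.82 to 0.86
- 30% stopping with an extra 20 mg/day: 0.46 to 0.53
- 30% stopping with an extra 40 mg/day: 0.27 to 0.30 (SE with/without 0.96 to 0.97)

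**Chance imbalance.** In the first simulation the arm difference in baseline dose after stratum adjustment had SD 0.6 to 1.3 mg/day and exceeded 1 mg/day in 8 to 44% of randomizations.

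**The case against.** **This is efficiency, not error.** The endpoint is one of six secondaries, without multiplicity control, in a trial whose primary objective is safety. The SAP is also internally coherent: a cumulative total has no baseline value of the same variable. This stands and limits the weight of the point. But daily dose is the obvious baseline counterpart, and the protocol's study summary describes ANCOVA with baseline scores for continuous endpoints. The protocol gives the SAP precedence, so this is not a violation; still, SAP section 8 declares no departure and no reason is given.

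**The size is assumed.** This also stands. Under heavy escalation after stopping, the gain nearly vanishes. No scenario showed a loss, but every simulated history starts at the baseline dose. The case shown in milligrams is more favourable than the medians (1.7 against 1.4 with all observed data; 2.4 against 2.2 with the cut).

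**Whether parenteral doses count is open.** The protocol summary lists oral and parenteral dose, and SAP 15.6 converts injectable forms. SAP 7.2, however, describes a summary of oral exposure while on treatment. The assumed courses are also far above the permitted single intramuscular dose (160 mg × 1.25 = 200 mg). Counting them only shrinks the gain, and both versions are shown.

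**Unbiased applies only to the omitted covariate.** If totals are truncated 28 days after stopping, unequal discontinuation biases them: about 68 mg at an assumed 8 mg/day with 10% against 25% stopping. The conflict between SAP 7.6 and SAP 7.4.2/Table 2 is a separate issue that the covariate does not solve.

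**Conclusion.** The concern holds. The model omits a predictor that the protocol's own dosing rules make strong, and the strata recover only part of it. The omission alone introduces no bias and does not disturb coverage; the loss is precision, together with an estimate that is hard to interpret under chance imbalance.

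Confidence is high in the omission and its direction, and low in the exact size. The standard error is inflated by anything from about 3% to a factor of 5. The main unknown is steroid use after study drug stops; dose spread, parenteral use, bursts and tapers also matter. It is worth correcting because the most the covariate can be expected to cost is under 1% of the standard error.

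**What to change.** In SAP 7.6.2, before unblinding, specify ANCOVA for cumulative prednisone-equivalent dose with treatment, the stratification factors and baseline daily prednisone-equivalent dose as a continuous covariate.

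Add a derivation rule for the covariate:
- Baseline is the stable daily dose in use immediately before the first study dose, converted with SAP Appendix 15.6, and 0 if none.
- A steroid recorded as ongoing before Day 1 keeps its recorded dose even if its start date is partial or missing. SAP Table 7 can impute such a date to the randomization visit. The SAP does not say that this sets baseline to 0, but the rule should exclude that reading. If it happened in 10% of steroid users, the ratio for 20% stopping and 25% of those escalating would fall from 2.03–2.54 to 1.48–1.62 with the cut, and from 1.33–2.00 to 1.20–1.45 with all observed data.
- Single parenteral or depot doses before Day 1 are not converted to a daily dose.

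The cost is one degree of freedom and this short rule. Baseline dose is already needed for the rescue criteria in SAP 6.21 and the 5 mg/day stratum threshold. The Table 2 estimand does not change, and the same model serves under either reading of the data cut.
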